## PROCEDURES:

Recruitment. Participants will be recruited during PHP treatment. As standard clinical care, all patients are screened for smoking status upon admission. Current daily smokers will be informed about the study at that time and invited to be screened for participation. All women of childbearing potential who would like the nicotine patch will complete a pregnancy test prior to inclusion into the study. Eligible and interested participants will complete an enrollment/pre-quit visit while enrolled in the PHP, which includes a baseline assessment, random assignment to a condition, the first counseling session and 4 weeks of nicotine patches (to be started on the quit day). The enrollment visit can be on the same day as the first pre-quit visit counseling but doesn't need to be. Participants will then complete a second pre-quit counseling session (within one week of the pre-quit session but before discharge). If the participant is to be discharged before their first or second counseling session, the counselor will choose one of the following options in order of preference ((1) complete the second counseling session early but not on the same day as the first counseling session,(2) have the patient return to the partial hospital program location for the first or second counseling session, (3) complete the counseling session by phone and mail materials distributed during the counseling session). Following the second counseling session, participants will continue in their assigned post-discharge intervention consisting of up to 5 Quitline or ACT telephone sessions.

Study outcomes will be assessed at the end of the counseling treatment at an in-person visit 5 weeks after their visit 2 date OR 24 hours after the last counseling session by a research staff member, whichever is later. As an incentive for completion of the follow-up assessment, those in either group who complete this visit will receive \$20 compensation and an additional 4 weeks of the nicotine patch. We will try to schedule visits around existing appointments in the hospital system to increase compliance.

Randomization will use block randomization, unknown to the counselor or the participant. In order to balance any benefit of bupropion treatment in combination with the nicotine patch across treatment conditions, randomization will be stratified by bupropion use.

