ACT Care (AC). Participants in the AC condition will receive one in-person and 6 telephone contacts delivered from an ACT framework. Sessions will last approximately 30 minutes. If the participant is unexpectedly discharged before their first counseling visit, the counselor will choose one of the following options in order of preference ((1) have the patient return to the partial hospital program location for the counseling session, (2) complete the counseling session by phone and mail materials distributed during the counseling session). This intervention is an adaptation of the in-person and telephone protocols developed by consultant [name] to deliver an ACT-based smoking cessation treatment to patients with bipolar disorder. This treatment was found to be feasible to deliver both in person (80% retention, 40% verified abstinent at end of treatment, 90% satisfied with treatment) and by telephone (67% retention, 33% verified abstinence, 100% satisfied with treatment).

The intervention targets the six core processes in ACT: acceptance, cognitive defusion, awareness of the present moment, self as context, defining values, and committed action towards values. In ACT, acceptance means increasing willingness to fully engage in all aspects of experience, as opposed to avoiding unpleasant experiences. Cognitive defusion refers to the separation of oneself from the content of one's thoughts, recognizing that cognition does not necessarily have to drive behavior (i.e., a patient can notice themselves having a thought and choose not to act on it).

Awareness of the present moment means being fully in contact with the present moment rather than dwelling psychologically in the past or the future (e.g., rumination about past failures or worry about future challenges). Self as context refers to the awareness that there is a self, independent of the content of thoughts or experiences that acts as an observer of these events.

Defining values is the process of identifying what is meaningful to individuals. Finally, committed action means making concrete value driven behavior change (as opposed to behavior driven by avoidance). The intervention relies heavily on experiential in-session exercises and metaphors as a means of helping smokers learn *in vivo* to apply ACT principles to the task of quitting smoking.

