#### Measures.

Feasibility, acceptability and safety. Feasibility of recruitment and retention will be measured by the proportion of smokers seen in the program during the enrollment period who enroll during the recruitment period. The two existing studies of smoking cessation treatment provided in inpatient psychiatric hospitals reported 69-79% recruitment rate (of those meeting inclusion criteria) and 80% retention. Results in this range will be considered feasible. Feasibility of treatment delivery will be assessed by the number of completed visits in the ACT group. Previous studies of ACT for tobacco cessation have found approximately 65-67% of calls were completed. Results in this range will be considered feasible. Acceptability will be measured at end of treatment using the 8-item Client Satisfaction Questionnaire (CSQ), a reliable and valid questionnaire developed to test health program acceptability. Safety. We will collect information on patient re-hospitalization via chart review and using questions from the 2016 National Health Interview Survey about visits to the emergency room and to the hospital. In addition, we will assess for symptom exacerbation. In addition, we will measure global distress using the K6 scale, a measure of non-specific psychiatric distress that has been used in population samples to discriminate between samples with and without mental illness.

Efficacy. Efficacy will be measured by 7-day point-prevalence tobacco abstinence at end of treatment, verified by an expired breath CO rating  $\leq 6\text{ppm}$ . Finally, we will assess number of serious quit attempts ( $>24$  hours of intentional abstinence).

ACT treatment targets. ACT treatment targets will be measured at both in person visits and during the follow-up call. The two overarching constructs of ACT, acceptance, and commitment will be assessed. Acceptance, will be measured using the Avoidance Inflexibility Scale (AIS), a 13 item, Likert scale, assessing participants' responses to their internal stimuli, including smoking-related thoughts, feelings and physiological sensations. Acceptance has been shown to account for the bulk of the treatment effect of ACT for tobacco cessation in previous studies. Commitment will be measured using the 8-item, Commitment to quitting scale (CTQ).

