Study Title: Acceptance and Commitment Therapy for Tobacco Cessation Among Psychiatric Partial hospital Patients

NCT#: NCT03911960

Date: July 1st, 2020

Data analysis.

Due to small sample sizes, analyses will be descriptive.

Aim 1. To assess the feasibility of the proposed ACT-based counseling program, we will conduct descriptive statistics on number of patients recruited to the program during the enrollment period compared to number of smokers seen in the PHP during the enrollment period. In addition, we will conduct descriptive statistics on the number of sessions completed per group and rates of completion of the follow-up visit. To assess acceptability of the program, we will report descriptive statistics of responses on the Client Satisfaction Questionnaire in each group. To evaluate the safety of offering a tobacco cessation intervention during a PHP, we will report on the number of participants in the trial who are rehospitalized for a psychiatric reason during the treatment period based on participant self-report at end of treatment. To assess for symptom exacerbation we will report means of psychiatric symptoms by group pre and post intervention among those who completed follow-up.

Aim 2. To evaluate for preliminary evidence of efficacy, we will report abstinence rates by group at end of treatment. Those lost to follow-up will be considered smokers.

Aim 3. To assess for the effect of treatment condition on ACT treatment targets, we will report descriptive statistics of treatment targets before treatment and at follow-up for those who completed the follow-up visit.

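### The SAP's psychiatric rehospitalisation count rests on end-of-treatment self-report and leaves out the chart review that the protocol plans, so participants without that self-report drop out of the safety count

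*SAP*

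**What the plan says.** The SAP's Aim 1 has two safety summaries. The first is the number of participants "rehospitalized for a psychiatric reason during the treatment period based on participant self-report at end of treatment". The sentence names no other source, no denominator and no split by group. The second, for symptom exacerbation, is "means of psychiatric symptoms by group pre and post intervention among those who completed follow-up".

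The protocol's Measures section (paragraph on feasibility, acceptability and safety) is broader on the first item: "We will collect information on patient re-hospitalization via chart review", together with national health survey questions on emergency room and hospital visits.

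The protocol's Procedures section (Recruitment) says that study outcomes are assessed "at an in-person visit 5 weeks after their visit 2 date OR 24 hours after the last counseling session", taking the later of the two.

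On incomplete follow-up, Aim 1 of the SAP reports "rates of completion of the follow-up visit", and Aim 2 sets a rule for abstinence: "Those lost to follow-up will be considered smokers". It sets no rule for rehospitalisation.

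**The concern.** A count built on self-report at the last assessment can include only people who gave one. A participant who was admitted and then lost contact does not appear in it. The chart is the one planned source that does not depend on the participant coming back, and the SAP does not use it.

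This count is the SAP's main evidence on whether it is safe to offer cessation treatment during partial hospitalisation. The protocol's Risks section itself treats these participants as prone to further acute episodes. With 40 participants, few admissions are to be expected and each missed one changes the picture. The symptom means cannot fill the gap, because they too cover only participants who completed follow-up.

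**Working it through.** **Sources side by side**

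| | Protocol, Measures | SAP, Aim 1 |
|---|---|---|
| Self-report | yes (survey questions) | yes, at end of treatment |
| Chart review | yes | not mentioned |
| Rule for those without self-report | none | none |
| Denominator | not stated | not stated |

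The plan gives no figure for rehospitalisation, so there is none to reproduce. The arithmetic below only sizes the group left out.

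**Inputs**
- N = 2 × 20 = 40 (protocol, Subject Recruitment, sample size).
- Retention r = 80%: the earlier inpatient trials "reported 69-79% recruitment rate (of those meeting inclusion criteria) and 80% retention" (protocol, Measures). The protocol's Interventions section gives the same 80% for in-person ACT.
- Low case r = 67%: the earlier ACT study "by telephone (67% retention, 33% verified abstinence, 100% satisfied with treatment" (protocol, Interventions, ACT Care).

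**Step 1. Participants outside the count** = N × (1 − r)
- r = 0.80: 40 × 0.20 = 8
- r = 0.67: 40 × 0.33 = 13.2, about 13

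**Step 2. Bounds that assume no admission rate.** If c admissions are reported, the true number lies between c and c + N(1 − r).
- r = 0.80, c = 0: 0 to 8 of 40 (0% to 20%)
- r = 0.80, c = 3: 3 to 11 of 40 (7.5% to 27.5%)
- r = 0.67, c = 0: 0 to about 13 of 40 (0% to 32.5%)

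The upper ends require every participant without a self-report to have been admitted. They are limits, not forecasts.

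**Step 3. Expected share missed, under an assumption.** Let k be the admission risk of those without a self-report, divided by the risk of those with one. The documents do not give k. The share of admissions missed is (1 − r)k / [r + (1 − r)k], whatever the underlying risk.

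| r | k = 1 | k = 2 | k = 3 |
|---|---|---|---|
| 80% | 0.20/1.00 = 20% | 0.40/1.20 = 33% | 0.60/1.40 = 43% |
| 67% | 0.33/1.00 = 33% | 0.66/1.33 = 50% | 0.99/1.66 = 60% |

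At k = 1 only the raw count is low; a proportion among those who reported would be unbiased. If k exceeds 1, that proportion is too low as well. If none of those left out was admitted (k = 0), nothing is missed.

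**Step 4. The time window.** A chart search needs an end date that exists for everyone. The protocol's Procedures section does not supply one. The second counselling session falls within one week of the first, and the outcome visit is 5 weeks after visit 2 or a day after the last session, the later of the two. But the first session need not fall on the enrollment day, and no limit is set on that gap. So 1 + 5 = 6 weeks cannot be counted from enrollment. For someone who stops counselling early or runs late, the due date of the visit is also unclear.

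**The case against.** - **Self-report need not be in person.** A reader might infer that anyone who misses the visit cannot be counted. The documents do not go that far. The SAP says only that the self-report is at end of treatment. The in-person setting comes from the protocol's Procedures, while Measures mentions a follow-up call for the ACT treatment targets. Some non-attenders might therefore still report by telephone. This stands: the group left out is those with no end-of-treatment self-report, and treating it as equal to non-attenders in Step 1 is an approximation.
- **Serious adverse events are reported anyway.** The protocol's Monitoring section sends every serious event, related or not, to the IRB and the funder, with quarterly review that includes an independent reviewer. So it would be wrong to infer that safety oversight depends on this count. But the SAP does not feed those reports into the count, and the count is the point here.
- **Follow-up completion is reported.** This shows how many lack data, but not what happened to them.
- **It is a small descriptive pilot with no safety threshold tied to this count.** This is true, and it limits the consequences. The point concerns who is counted, not power or testing.
- **The later SAP may have narrowed the source deliberately.** The protocol is dated September 2019 and the SAP July 2020, so this is possible. The SAP gives no reason, however, and does not say that chart collection was cancelled.
- **The comparisons with other outcomes prove little.** Symptom means need the participant's answers, so limiting them to completers is not a like omission. Counting lost participants as smokers does not imply a matching rule for admissions. Both points are fair, and the conclusion does not rest on either.
- **Charts may add little.** No chart coverage is stated, and the releases described are for informing providers, not for obtaining outside records. This stands, and it is why the number with neither source must be shown.

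**Conclusion.** The point holds. As written, the SAP bases its rehospitalisation count on one of the two sources that the protocol plans, and participants without an end-of-treatment self-report are left out: about 8 of 40 at 80% retention, about 13 at 67%. The count is too low if any of them was admitted.

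The size of the undercount is unknown. The bounds in Step 2 rest only on N and on retention figures from earlier studies. The percentages in Step 3 also rest on an assumed k. A reader might infer that admitted participants are less likely to return, and hence that a large share of admissions is lost. That is plausible, but the documents say nothing about how often admitted participants attend, so no such figure should be quoted as a finding.

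This does not undermine the trial. It is an avoidable gap in the analysis of its safety aim and should be closed.

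**What to change.** Replace the Aim 1 sentence with wording such as: *We will report, by group, the number of all randomised participants with a psychiatric rehospitalisation found by chart review or self-report within [fixed period] of randomisation.*

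- **Window:** one period, the same for everyone, chosen by the sponsor to cover the planned treatment period. Six weeks after enrollment should not be adopted by default (Step 4).
- **Sources:** name the hospitals that the charts cover. Show the number found by self-report only, chart only and both.
- **No information:** show the number with neither source. Do not treat the absence of a chart record as proof of no admission.
- **If chart review was dropped on purpose:** say so, and report the self-report count with the number of participants without data.

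The cost is one SAP sentence and a review of at most 40 charts, including a judgement on whether each admission was psychiatric. The protocol already plans the chart review, no extra visit is needed, and the work can be done after enrollment ends. The downsides are that charts may miss admissions to other hospitals and that the count mixes two sources, which is why the split by source has to be shown.

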## Interventions.

Nicotine patch. All participants will receive usual psychiatric care plus an offer of the nicotine patch (up to 8 weeks), dosed per package instructions. At the second pre-quit session, participants will be instructed on patch use. The first 4 weeks of patch will be distributed at enrollment and the second 4 weeks will be distributed at the follow-up visit.

Enhanced Usual Care (EUC). Participants in the EUC condition will receive one in-person counseling sessions during the PHP and a second telephone session the week following: the first session will occur prior to the quit day and will focus on establishing a quit plan and instructing the participant on the use of the nicotine patch; the second session will occur prior to quit day and will assess for any difficulties using the nicotine patch. After the second session, participants will be electronically referred to the RI state quitline. This quitline offers an enrollment call and 5 proactive counseling telephone counseling telephone calls to those who enroll. Quitline staff make up to 3 attempts per call to reach users. Total scheduled counseling time offered is 120 minutes. If the participant is unexpectedly discharged before their first counseling visit, the counselor will choose one of the following options in order of preference ((1) complete the second counseling session early but not on the same day as the first counseling session,(2) have the patient return to the partial hospital program location for the first counseling session, (3) complete the counseling session by phone and mail materials distributed during the counseling session).

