### PROTECTION AGAINST RISK:

Minimization of nicotine patch side effects: The nicotine patch is an over the counter medication with few serious side effects. However, participants will be screened for all contraindications to the patch. If a contraindication is present, they must obtain approval from a medical provider before participating. Participants will agree to consult with their outpatient medical providers regarding the safety of using the patch if their medical status changes after the patch is initially provided. Further, study counselors will explain the patch's purpose, application, and side effects, as well as how to use the patch in a manner that minimizes risk.

To minimize skin reactions, participants will be instructed to move the site of patch placement each day and to not repeat site use for at least one week. Patch dose may be adjusted downward if there is significant nausea or other reactions. Participants will be instructed to remove the patch before bed if it significantly interferes with sleep. Participants with severe side effects will be asked to discontinue patch use and contact their primary care provider before resuming.

Minimization of nicotine withdrawal symptoms after quitting: Participants that decide to use the nicotine patch will be told that it will reduce but not entirely eliminate withdrawal symptoms. Participants will be instructed to call their outpatient physician or psychiatrist in the case of severe withdrawal reactions. Withdrawal symptoms typically abate within 1 to 2 weeks of quitting and are not medically dangerous.

Minimization of risk from worsening of depression and emergent suicidality: There is no evidence indicating that participation in this trial will worsen depression or cause suicidality. In fact, other studies have found that quitting smoking is associated with improvements in psychiatric symptoms. However, given that participants will be enrolled during an acute psychiatric episode, it is likely that some participants will experience worsening of depression during this study. A minority may experience episodes of suicidal ideation. Thus, we will monitor and respond to these issues in an ethically sensitive manner.

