#### Monitoring.

[name] (PI) will have primary responsibility for monitoring all participants. Any data or safety issues that arise will also be discussed with [name], a senior investigator with extensive experience conducting tobacco cessation research with patients with mental illness, who will provide consultation. In addition, an independent faculty member will be recruited before the start of the study to serve as an independent reviewer. Drs. [name], [name], [name], and the independent reviewer will meet quarterly to review study progress and the occurrence of adverse events.

In addition, The Miriam Hospital IRB will initially approve the study. All needed changes or amendments to the IRB approved protocol will be submitted to the IRB in a timely manner. There will be no changes in protocol enacted until IRB approval of the new protocol is received.

[name] will report all adverse events to The Miriam Hospital IRB within 24 hours. The funding institution will be informed in cases when any significant action is taken as a result of an adverse event or by direction of the IRB. Any serious adverse event (SAE), whether or not related to study intervention, will be reported to both the IRB and the funding institution. A summary of the SAEs that occurred during the previous year will be included in the annual progress reports to both the IRB and the funding institution.

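### SAP Aim 1 counts psychiatric rehospitalisation from end-of-treatment self-report alone, although the protocol also plans chart review, so participants who do not return add nothing to the safety count

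*SAP*

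**What the plan says.** SAP Aim 1 has two safety summaries. For admissions, "we will report on the number of participants in the trial who are rehospitalized for a psychiatric reason during the treatment period", and the source is given as "based on participant self-report at end of treatment". For symptoms, "To assess for symptom exacerbation we will report means of psychiatric symptoms by group pre and post intervention among those who completed follow-up".

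The protocol names a wider source for admissions. Under Safety in its Measures section it says "We will collect information on patient re-hospitalization via chart review", and it adds National Health Interview Survey questions on emergency room and hospital visits. The SAP, dated after the protocol, does not mention chart review and gives no reason for leaving it out.

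On timing, the Procedures section says "Study outcomes will be assessed at the end of the counseling treatment at an in-person visit 5 weeks after their visit 2 date". The visit moves to one day after the final counselling contact where that is the later date.

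Separately, the Monitoring section says "Any serious adverse event (SAE), whether or not related to study intervention, will be reported to both the IRB and the funding institution". It also has adverse events reported to the IRB within 24 hours, and a quarterly review that includes an independent reviewer.

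**The concern.** Self-report at a visit exists only for people who attend it. Chart review is the planned source that does not need attendance, and the SAP omits it. If the SAP is followed as written, the rehospitalisation count is silent about everyone lost to follow-up. Someone who is in hospital when the visit falls due may well be among them; that is our inference, not a statement in the documents.

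This matters because Aim 1 is where the trial reports on the safety of offering cessation treatment during a partial hospital stay. The Protection Against Risk section acknowledges the vulnerability of this population: "participants will be enrolled during an acute psychiatric episode, it is likely that some participants will experience worsening of depression" (it also says there is no evidence that taking part causes this). For abstinence, the SAP states how people lost to follow-up are handled, namely as smokers. For rehospitalisation it states nothing comparable. A reader could take a low count as covering all 40 participants when it covers only those who came back.

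**Working it through.** **The texts side by side.** The protocol has two sources for rehospitalisation, charts and survey questions. The SAP has one, self-report at end of treatment. The protocol places outcome assessment at a single in-person visit. The Measures section mentions a follow-up call for the ACT treatment targets, but no section provides for safety data by telephone from people who miss the visit. A non-returner therefore has no rehospitalisation data under the SAP.

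**No planned figure to reproduce.** The documents give no expected rehospitalisation rate, and the SAP is descriptive. What follows only sizes the gap.

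**Inputs**
- Sample size: 20 per group, 40 in total (protocol, Subject Recruitment).
- Retention: 80% (benchmark in the Measures section). As a lower value, 67%, the retention reported under ACT Care for telephone delivery in an earlier feasibility study. Neither is an observed rate for this trial's visit.
- Two self-reported rehospitalised participants: our assumption, for illustration.

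**Non-returners** = 40 × (1 − retention)
- 80%: 40 × 0.20 = 8, leaving 32 returners.
- 67%: 40 × 0.33 = 13.2, so about 13, leaving 27 returners.

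**Range over all randomised** = x/40 to (x + non-returners)/40, with x = 2
- 80%: 2/40 = 5% to (2 + 8)/40 = 25%. Among returners alone, 2/32 = 6.25%.
- 67%: 2/40 = 5% to (2 + 13)/40 = 37.5%.

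The lower end assumes that no non-returner was rehospitalised, and the upper end that all were.

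**Expected share missed.** Let R be the follow-up share and RR the rehospitalisation risk in non-returners relative to returners. If self-report catches every event in returners, the share missed is (1 − R)RR / [R + (1 − R)RR]. At R = 0.80:
- RR = 1: 0.20/1.00 = 20%
- RR = 2: 0.40/1.20 = 33%
- RR = 3: 0.60/1.40 = 43%

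RR is assumed. The first line shows that some undercount is expected even if non-returners are no sicker than returners.

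**What chart review changes.** The rehospitalisation count would cover 40 participants rather than about 32, for admissions visible in the charts reviewed. It would not supply end-of-treatment symptom scores for the 8 who did not return.

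**Symptom means.** A mean cannot show how many scores rose, but a count of rises is hard to read as well. Take normal changes, equal spread before and after, and a pre/post correlation r. The SD of change is then √(2(1 − r)) in enrolment-SD units. With no mean change, a rise of at least half an SD has probability 1 − Φ(0.5/√(2(1 − r))): 34% at r = 0.3, 31% at r = 0.5 and 21% at r = 0.8. Falls of that size are equally common. The documents give no value of r.

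**The case against.** This is a 40-person pilot, the SAP says its analyses are descriptive, and no decision rule depends on the rehospitalisation count. The SAP also reports follow-up completion, so the extent of non-return will be visible. All of that stands, and it limits the weight. It does not explain why a planned source that could cover non-returners is left out.

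A reader might infer that rehospitalisations of non-returners would escape all oversight. The documents do not support that. The Monitoring section requires adverse events to go to the IRB, SAEs to go to the funder as well, and a quarterly review with an independent reviewer. What remains is that the SAP does not bring those data into Aim 1.

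A reader might also fault the SAP for not splitting rehospitalisation by arm. The stated question is the safety of offering cessation treatment in this setting, and both arms are offered it: "All participants will receive usual psychiatric care plus an offer of the nicotine patch". A pooled count fits that question.

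Finally, a reader might infer that completer means conceal harm. The SAP declares the restriction openly, and no reanalysis recovers scores that were never taken. Individual changes in arms of this size could not compare the arms or attribute worsening to treatment. Fuller symptom reporting is therefore a preference, not a correction.

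**Conclusion.** The mismatch is real. The SAP's source for rehospitalisation is narrower than the protocol's, and the part left out is the part that could reach people who miss the visit. The count can be too low. How far depends on the number who do not return and on their risk, neither of which the documents give. The 5% to 25% range rests on 80% retention borrowed from other studies, two assumed events and a worst-case upper end; it shows what the planned report would leave open and is not a forecast.

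The order of the documents might suggest a deliberate decision to drop chart review. The SAP gives no reason, so it cannot be told apart from an omission.

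The weight is minor to moderate. The sources should be reconciled before results are reported.

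**What to change.** Amend SAP Aim 1 to match the protocol's Measures section:

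1. Count psychiatric rehospitalisation from chart review and self-report together, for all randomised participants.
2. Fix one chart window, defined the same way for everyone, for example a set number of days from randomisation chosen by the study team. It should not depend on attending the visit or on the last counselling session. The visit rule in the Procedures section will not serve: the due date may be undefined for someone who never had visit 2, and staff may not know when an outside quitline's last call took place.
3. Report the count by source (self-report only, chart only, both), with the number who have neither. A split by arm is useful but optional.

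Optionally, beside the symptom means, show individual changes and the number with no end-of-treatment score. The SAP does not name the scale; K6 is the only psychiatric symptom scale in Table 2, so presumably K6 is meant. Describe these as score changes, not as evidence of harm or a comparison of arms.

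The cost is a modest amount of chart abstraction that the protocol already plans, plus a small table. Charts may miss admissions elsewhere, which is why the count should be shown by source.
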